6.2 Study setting

Patients will be seen in-person at the Gastroenterology Department of any of the study centres that will participate in patient recruitment (Mediclinic City Hospital, Mediclinic Parkview Hospital and Rashid hospital) by one of the coninvestigator consultant gastroenterologists at screening and randomization (T0), at a follow-up visit at 3 months (T1), and at a second follow-up visit at 6 months (T2). Routine blood tests as well as an extra sample for research

RJ

Version 3.2. Effective Date: 04 December 2021

purposes will be obtained at these timepoints. Colonoscopies will be performed as part of the routine clinical practice and these include acquisition of routine biopsies, typically 10-15 from each patient. A few additional biopsies (2-4) will be needed for our studies, to be snap frozen and analyzed in MBRU research laboratory facilities. IRB approval for these additional biopsies and serological testing is being sought from both Mediclinic City Hospital's REC, MBRU-IRB and DHA-REC. It is hoped that the routine colonoscopies can be scheduled prior to starting the study treatment and 6 months later.

6.3 Sample and recruitment

All eligible IBD patients visiting Gastroenterology Department of any of the study centres that will participate in patient recruitment (Mediclinic City Hospital, Mediclinic Parkview Hospital and Rashid hospital) under the care of any of the coinvestigator consultant gastroenterologists during the period of recruitment (12 months from the start date of the study – to be decided following ethical approval) will be offered to take part in the study.

Block randomization over four blocks of 25 patients will be used to ensure an equal number of patients in each treatment group, even if the trial was terminated early for any reason. Two blocks will be reserved for patients with quiescent/minimal disease and two blocks for patients with mild disease, in order to ensure an equal number of these patients in each treatment group. Patients will be randomised (1:1) to receive Frondanol (one 1000 mg capsule twice daily) or placebo (in a similar capsule) as an adjunct to their standard therapy using a randomization number sequence generator. This will be conducted by the study statistician using the Microsoft Excel random number generator and will only be shared with the study coordinator.

All patients and investigators, excluding the study coordinator, will be blinded to treatment allocation. Frondanol and placebo capsules will be placed in identical-looking vials which will be labelled with the study name and number, and no identifying information. The labelling of the vials will be done with the open randomization sheet by the study coordinator. When a patient agrees to participate, and signs the informed consent form, the physician will assign to the patient the next available randomization number from the randomization sheet (supplied by the study coordinator) with the corresponding labelled medication vial. Patients will be instructed to take one capsule of their assigned medication twice daily. Hence, capsules will be given in a double-blind manner where patient and physician are not aware of treatment allocation as the treatment and placebo vials will only indicate the pilot study name. Investigators involved in the laboratory analysis of samples will also be blinded, they will only know if a patient belongs to group 1 or 2 but will not know which group is taking Frondanol and which is taking placebo.

RJ

Version 3.2. Effective Date: 04 December 2021

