1. PROTOCOL SUMMARY

Study Title	A pilot randomized, double-blind, placebo-controlled trial to investigate the anti-inflammatory effects of Frondanol in adults with inflammatory bowel disease
Internal ref. no. (or short title)	Frondanol in IBD
Study Design	This is a pilot, prospective, double-blinded, two-arm, randomized controlled trial of the efficacy of Frondanol in comparison to placebo in decreasing bowel inflammation in patients with a clinical diagnosis of IBD who are in remission and on standard of care treatment.
Study Participants	
Inclusion criteria: A confirmed clinical diagnosis of IBD of any duration, age 18 years or older, with mild to moderate disease and on standard therapy. The diagnostic criteria for IBD include the presence of chronic diarrhoea for more than four weeks, and evidence of active inflammation on endoscopy and chronic changes on biopsy. Patients with stable mild to moderate IBD will be eligible for the study. Stable IBD is defined as having stable symptoms over a period of several weeks, diagnostic evaluation has been completed and the patient has been on consistent medication. Mild to moderate IBD is indicated by a Partial Mayo score (Mayo Clinic Score/Disease Activity Index for Colitis) of between 1-6, and a total of Mayo score of 1-10 (Pabla and Schwartz, 2020). For patients with Crohn's disease, only those with Crohn's colitis will be included (patients with small bowel disease are eligible to enter the trial as long as they also have large bowel inflammation).
 
Exclusion criteria: Pregnancy, breastfeeding, allergy to seafood or marine products, severe medical illness such as uncontrolled diabetes ($\text{HbA1C} > 10$), significant or unstable cardiovascular or pulmonary disease, impaired renal function ($\text{Cr} > 2.0 \text{mg/dL}$), current or recent ($< 1 \text{ year}$) malignancy, or other significant medical illness that in the view of the investigators may impair participation in the study. Patients with severe IBD (defined by a Partial Mayo score of 7-9 and a total Mayo score of 11-12 (Pabla and Schwartz, 2020), with active symptoms) will not be eligible to participate in the study.
 
Reference:

RJ

Version 3.2. Effective Date: 04 December 2021

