6.5 Eligibility criteria

- **Inclusion criteria:**

A confirmed clinical diagnosis of IBD of any duration, age 18 years or older, with mild to moderate disease and on standard therapy. The diagnostic criteria for IBD include the presence of chronic diarrhoea for more than four weeks, and evidence of active inflammation on endoscopy and chronic changes on biopsy. Patients with stable mild to moderate IBD will be eligible for the study. Stable IBD is defined as having stable symptoms over a period of several weeks, diagnostic evaluation has been completed and the patient has been on consistent medication. Mild to moderate IBD is indicated by a Partial Mayo score (Mayo Clinic Score/Disease Activity Index for Colitis) of between 1-6, and a total of Mayo score of 1-10 (Pabla and Schwartz, 2020). For patients with Crohn's disease, only those with Crohn's colitis will be included (patients with small bowel disease are eligible to enter the trial as long as they also have large bowel inflammation).

- **Exclusion criteria:**

Pregnancy, breastfeeding, allergy to seafood or marine products, severe medical illness such as uncontrolled diabetes ($\text{HbA1C}>10$), significant or unstable cardiovascular or pulmonary disease, impaired renal function ($\text{Cr}>2.0\text{mg/dL}$), current or recent (<1 year) malignancy, or other significant medical illness that in the view of the investigators may impair participation in the study. Patients with severe IBD (defined by a Partial Mayo score of 7-9 and a total Mayo score of 11-12 (Pabla and Schwartz, 2020), with active symptoms) will not be eligible to participate in the study.

Reference:

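### Section 6.3 reserves all 100 places under severity labels that have no cut-points and do not match eligibility; as a lesser matter, blocks of 25 cannot keep the arms equal on early stopping

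*Combined protocol and SAP*

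**What the plan says.** Section 6.3 sets the allocation scheme: "Block randomization over four blocks of 25 patients will be used to ensure an equal number of patients in each treatment group", and adds "even if the trial was terminated early for any reason". It then divides the blocks by severity: "Two blocks will be reserved for patients with quiescent/minimal disease and two blocks for patients with mild disease", with the stated purpose "in order to ensure an equal number of these patients in each treatment group". At enrolment, "the physician will assign to the patient the next available randomization number from the randomization sheet". The same section offers entry to all eligible patients at the participating centres.

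Eligibility is worded differently. The protocol summary (section 1) and section 6.5 both state: "Patients with stable mild to moderate IBD will be eligible for the study". Section 6.5 defines the band by score: "Mild to moderate IBD is indicated by a Partial Mayo score (Mayo Clinic Score/Disease Activity Index for Colitis) of between 1-6", with a total Mayo score of 1-10. Only severe disease is excluded on activity (Partial Mayo 7-9 and total Mayo 11-12). The study design row of section 1, section 3, the design overview (numbered 5.1, within section 6) and section 6.4 describe patients in remission.

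Sections 6.6 and 8.1 repeat the randomisation text without blocks or strata. Section 8.2 names age and sex as examples of adjustment factors and does not mention the stratum. Section 6.12 lists poor enrolment as a ground for ending the study early.

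**The concern.** There are two separate problems, of unequal weight.

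The first is the strata. The two labels take up the whole sample, neither has a score attached, and neither is the label used for eligibility. A physician with a consenting patient must choose a list before taking the next number, and the protocol gives no rule for that choice. Centres may then turn eligible patients away or place similar patients on different lists. Stratification by severity would not do what section 6.3 intends, and the severity mix of the recruited sample would be hard to describe.

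The second is the block size. An odd block cannot split 1:1, and large blocks allow a sizeable arm difference part-way through. Equality on early termination is promised outright, and the plan itself foresees an early stop.

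**Working it through.** **Total.** 4 x 25 = 100, which matches the 100 patients (50 per arm) in section 6.4.

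**Strata.** Places reserved: 2 x 25 = 50 quiescent/minimal and 2 x 25 = 50 mild, so 100 of 100. The severity wording, side by side:

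| Place | Wording | Score given |
|---|---|---|
| Section 1, study design | in remission | none |
| Section 1, participants; section 6.5 | stable, mild to moderate | Partial Mayo 1-6, total 1-10 |
| Section 3; design overview (5.1) | in remission | none |
| Section 6.3 | quiescent/minimal; mild | none |
| Section 6.4 | stable, in remission | none |

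If *mild* excludes *moderate*, the places left for eligible moderate patients are 100 - (50 + 50) = 0. If *mild* is meant to cover the rest of the 1-6 band, the boundary between the two lists is still missing. At the lower end, a quiescent list sits beside an entry floor of 1, and the plan does not say how the two fit. The documents give no share of moderate patients, so the number affected cannot be estimated.

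**Blocks, full enrolment.** 25/2 is not an integer, so the closest split is 13:12. If a stratum's two blocks offset, 13 + 12 = 25 against 12 + 13 = 25, and the stratum ends 25:25. The plan does not state this rule. If each block's direction were random, a stratum would end 25:25 with probability 2/4 = 50%. The trial would end 50:50 with probability 6/16 = 37.5%, and could end as far apart as 48:52.

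**Blocks, early stop.** Assumptions: offsetting blocks, direction of the first block random, and each patient equally likely to belong to either stratum (binomial count, at most 50 per stratum). After k patients in a block of 25 with a places for Frondanol, the number x on Frondanol has

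P(x) = C(a, x) C(25 - a, k - x) / C(25, k), with arm difference d = 2x - k.

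Example: for a = 13 and k = 12, P(d = 0) = 1716 x 924 / 5,200,300 = 0.305. The two strata are combined by convolution. Relative to equal arms, the efficiency loss for a difference d among n patients is (d/n)^2; a 22:28 split at n = 50 loses (6/50)^2 = 1.44%.

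| Scheme | Result | n = 30 | n = 50 | n = 70 |
|---|---|---|---|---|
| Blocks of 25, offsetting | arms equal | 22.4% | 33.0% | 23.3% |
| | difference of 4 or more | 39.3% | 20.9% | 37.5% |
| | mean efficiency loss | 1.40% | 0.26% | 0.24% |
| | largest possible difference | 22 | 26 | 22 |
| Blocks of 10 | arms equal | 41.3% | 44.0% | 45.0% |
| | difference of 4 or more | 12.9% | 11.4% | 10.9% |
| Five 4s and five 6s, random order | arms equal | about 55% | about 55% | about 55% |
| | difference of 4 or more | 2.3% | 2.3% | 2.3% |

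With 30% to 50% of patients in one stratum, blocks of 25 give equal arms in 22% to 33%, a difference of 4 or more in 20% to 39%, and a mean loss of 0.1% to 1.4%. A difference of 13 within one stratum can occur only at exactly 13 or 37 patients in it. The overall maximum of 26 therefore needs 13 + 37 = 50 patients (or 13 + 13 = 26, or 37 + 37 = 74) and is very unlikely.

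**The case against.** On the strata, the sponsor may have meant *mild* to include moderate disease. Section 6.5 takes its severity bands from a cited review that is not part of the documents, so intended cut-points cannot be ruled out. This stands. A reader might infer that moderate patients are shut out of the trial; the documents do not establish that. It is only the natural reading of *mild*, and sections 1 and 6.5 admit these patients. The certain defect is that the labels are undefined and conflict.

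A reader might also infer that balance within strata cannot be achieved until the strata are defined, or that the treatment comparison is biased. Neither follows. The 25:25 split on each list comes from the list and does not depend on the cut-point. A patient placed on the wrong list is still randomised 1:1. The harm is operational, together with a stratification factor that does not measure what it names.

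On the blocks, four groups of 25 could describe a two-by-two layout: 25 patients per arm at each severity level. That fits 50 per arm and removes the odd-block difficulty at completion, as offsetting blocks also would. So the text does not show that the final arms must be unequal. It does not rescue the early-termination promise, which no block size could keep at every stopping point. The efficiency loss is small, and the choice among smaller even blocks is partly a design preference.

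**Conclusion.** Both parts hold, and the point as a whole should be fixed because of the strata. It is certain from the text that all 100 places are reserved under two labels without cut-points, and that the protocol describes its population in three ways that are not mapped to one another. How many patients this affects is unknown.

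The block-size part would be minor on its own. The promise of equal arms on early termination is wrong as written: equality holds in roughly a fifth to a third of the stops examined. There is no bias, and the mean efficiency loss is at most about 1.4%. These figures assume offsetting blocks and a stratum share of 30% to 50%.

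**What to change.** **Strata.** The sponsor should reconcile the severity wording in sections 1, 3, 5.1 (design overview), 6.3, 6.4 and 6.5; this review does not say which population is right. The strata should then be defined by score so that every eligible patient falls in exactly one. Whether to keep 50 places per stratum is the sponsor's choice. If the change is substantial, section 10.7 requires submission to the ethics committee before implementation.

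**Blocks.** Use permuted blocks of even size within each stratum, keep the sizes undisclosed to sites, and replace the promise of equality with the bound the blocks give. Two schemes fill 50 places and end at 25:25 per stratum:
- five blocks of 10: difference at most 5 per stratum, 10 overall;
- five blocks of 4 and five of 6 in random order (20 + 30 = 50): at most 3 per stratum, 6 overall.

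If 50 places per stratum are not kept, the last block may be incomplete and the final arms may differ by up to the same bound.

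**Cost.** A new list and a wording change, with no extra patients or procedures. The drawback is predictability. If block sizes and earlier allocations became known, the next allocation would be certain for about 1.86/25 = 7% of patients with blocks of 25, 1.67/10 = 17% with blocks of 10, and (5 x 1.33 + 5 x 1.5)/50 = 28% with the mixed set.

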Planned Size of Sample (if applicable)	100 patients (50 per arm) with stable IBD will be recruited into this pilot study.
Follow up duration (if applicable)	Six months
Planned Study Period	Two years
Research Question/Aim(s)	
1) To compare plasma levels, biopsy mRNA (using low density expression arrays) and protein (using either Luminex or Western blotting) levels of the following parameters between IBD patients treated with Frondanol and those treated with placebo at baseline and after six months of treatment:
 
a) Cytokines: TNFα, IL1β, IL6, IL17A, IL21, IL22, IL23, IFNγ, IFNα, as well as vascular endothelial growth factor (VEGF-A), MIP-1, MIP-2;
 
b) Markers of inflammation: Myeloperoxidase, calprotectin, S100A12, β2-microglobulin, amyloid A (A-SAA), intercellular adhesion molecule 1 (ICAM-1), vascular cell adhesion molecule 1 (VCAM-1), MIP-2α (CXCL2), MCP-1 (CCL2). Leukotriene B4 (LTB4), 5-hydroxyeicosatetraenoic acid (5-HETE) and prostaglandin E2 (PGE2) will be measured by specific ELISA assays.
 
2) To compare the following routine clinical parameters between IBD patients treated with Frondanol and those treated with placebo at baseline and after six months of treatment:
 
a) Patient symptoms;
 
b) Blood: Complete blood count (CBC), erythrocyte sedimentation rate (ESR), C-reactive protein (CRP), albumin;
 
c) Stool: Fecal calprotectin level;
 
d) Endoscopic and histologic features.
 
3) To compare in-vitro concentration-dependent responses to Frondanol and placebo on inflamed organoids by measurement of cytokines and other inflammatory markers, in particular 5-HETE, LTB4 and PGE2.

RJ

Version 3.2. Effective Date: 04 December 2021

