8.2 Statistical methods

All statistical analyses will be carried out using SPSS Software (Armonk, New York, USA). Potential confounders such as age and sex will be controlled for during the analysis phase. A per-protocol analysis including only participants who have a full data set will be used to assess the efficacy of Frondanol treatment in lowering inflammatory markers. An intention-to-treat analysis will also be conducted including patients who drop out before the study ends, for whom we will use last observation carried forward (LOCF) i.e. we will impute the last observed data for all subsequent (missing) observation points. For quantitative data, within-group and between-group comparisons will be analyzed using the General linear Repeated Model (MANOVA), which would allow for adjustment of potential confounders such as age and sex. Data will be plotted as mean \pm SEM and p values <0.05 will be considered statistically significant.

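### Hospital is neither a randomisation factor nor a named model term, and the severity stratum is not a named model term: a modest, avoidable loss of balance and precision, not a threat to validity

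*Combined protocol and SAP*

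**What the plan says.** The Protocol Summary fixes the size: "100 patients (50 per arm) with stable IBD will be recruited into this pilot study". Sections 6.2, 6.3 and 6.4 name three recruiting centres ("Mediclinic City Hospital, Mediclinic Parkview Hospital and Rashid hospital").

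Section 6.3 sets out the allocation: "Block randomization over four blocks of 25 patients will be used to ensure an equal number of patients in each treatment group". The only stratification factor is severity: "Two blocks will be reserved for patients with quiescent/minimal disease and two blocks for patients with mild disease". At enrolment, "the physician will assign to the patient the next available randomization number from the randomization sheet" and hands over the vial carrying that number. The study coordinator labels the vials and supplies the sheet. The section does not describe a list or block for each hospital, or how one sequence is run across three sites.

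Section 8.2 plans a repeated-measures general linear model and says: "Potential confounders such as age and sex will be controlled for during the analysis phase". Neither hospital nor the severity stratum is mentioned. Section 8.1, despite its title, gives no effect size, SD or power. No section gives expected numbers per hospital or a between-hospital variance.

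**The concern.** Two features combine. Randomisation seeks balance over the whole trial and within severity, but not within hospital, so one hospital can by chance contribute clearly more patients to one arm. The analysis, as named, then does nothing to remove hospital differences. It also omits the severity stratum, although the allocation was restricted on it.

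Hospitals may differ in case mix and background therapy, because standard therapy continues unstandardised. They may also differ in local measurement: in section 6.14, Table 1 places the faecal calprotectin assay at the recruiting hospital and Table 2 places it at one named hospital, and the two need reconciling. Where such differences exist, they widen the interval for the arm comparison, and a chance imbalance shifts the estimate in the single trial that is run. Hospital and stratum are known for every patient at randomisation, so the loss is avoidable.

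**Working it through.** **Inputs from the documents.** N = 100, 50 per arm (Protocol Summary); three hospitals (6.2 to 6.4); four blocks of 25, two per severity stratum (6.3); significance at 0.05 (8.2), taken as two-sided.

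**Assumptions, because the documents give no figure.** Hospital sizes; between-hospital SD of 0.25, 0.4 or 0.7 of the residual SD; an effect of 0.57 residual SD, which has about 80% power with 50 per arm; correlation of 0.5 between visits.

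**1. The layout.** 4 x 25 = 100, which reproduces the planned total. No block is left over for any hospital, and 3 hospitals x 2 strata = 6 cells cannot each have a block when there are four. Sharing of blocks across hospitals is an inference from this arithmetic and from the single sheet; the text does not state it.

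**2. Chance imbalance within one hospital.** Take 33 of 100 patients at one hospital and 50:50 arms overall. The number on Frondanol there is hypergeometric (100, 50, 33).
- Variance = 33 x 0.5 x 0.5 x (100 - 33)/(100 - 1) = 8.25 x 0.677 = 5.58, so SD = 2.36.
- The arm difference is 2 x count - 33, so its SD is 2 x 2.36 = 4.7 patients.
- Probability of 20:13 or worse, in either direction: 20%.

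A simulation of the actual layout (6,000 trials per hospital split, blocks of 25 divided 12/13) gives the chance that at least one hospital has a large arm difference:

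| Assumed hospital sizes | 6 or more | 8 or more | 10 or more |
|---|---|---|---|
| 34/33/33 | 48% | 26% | 11% |
| 50/30/20 | 53% | 28% | 13% |
| 60/30/10 | 47% | 23% | 10% |

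With permuted blocks of 4 within hospital and stratum, no simulated trial reached a difference of 6.

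**3. What an imbalance does to the estimate.** If one hospital splits 20 v 14 and its mean differs from the others by 0.5 SD, the unadjusted arm difference moves by 0.5 x (20/50 - 14/50) = 0.06 SD. For a 1 SD hospital difference it moves by 0.12 SD.

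**4. Precision.** The intraclass correlation is s²/(1 + s²), where s is the between-hospital SD in residual SDs: 0.0625/1.0625 = 0.06, 0.16/1.16 = 0.14 and 0.49/1.49 = 0.33. Simulated power with hospitals of 50/30/20, without and then with hospital in the model:

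| Comparison | s = 0 | s = 0.25 | s = 0.4 | s = 0.7 |
|---|---|---|---|---|
| Six-month level | 81% to 80% | 79.1% to 79.6% | 76% to 79% | 71% to 80% |
| Change from baseline, constant hospital effects | – | – | 80% to 79% | 82% to 81% |
| Between-group main effect over all visits | – | – | 59% to 63% | 50% to 62% |

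With 6,000 runs, the simulation error of a power near 80% is about sqrt(0.8 x 0.2/6,000) = 0.5 points, so differences of about a point are small.

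The third row has lower power because the main effect averages in the baseline visit. With the full effect at both follow-up visits, the mean effect is 0.57 x 2/3 = 0.38. The SD of a three-visit mean is sqrt((1 + 2 x 0.5)/3) = 0.82. Power is then about 64%, in line with the adjusted figures.

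The second row shows no gain because a hospital effect that is the same at every visit cancels within the patient. Only hospital differences in change would remain in the error of the group-by-time contrast.

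**The case against.** The strongest case against the point is that it is small. The planned model is a repeated-measures one, and its group-by-time test already removes constant hospital differences, so a gain there requires hospitals to differ in change. Nothing in the documents shows that they do. At a between-hospital SD of 0.25, even the level comparison gains only about half a point. The covariate list in 8.2 is introduced with the words such as, so hospital is unnamed rather than excluded. Leaving hospital out of the stratification of a 100-patient pilot is also a defensible choice, since six cells bring more incomplete blocks. All of this stands, and it limits the size of the point. It does not remove it. An open covariate list leaves the choice until after the data are seen. The between-group main effect and any comparison of six-month levels do carry hospital variation.

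A reader might also infer stronger things that the documents do not support:
- **Each hospital has its own scorers.** Sections 6.2 and 6.4 say that patients are seen by one of the co-investigator gastroenterologists and do not tie assessors to sites.
- **Every endpoint is affected.** The research blood and biopsy assays are run in one university laboratory (6.2, 6.14).
- **Numbers will be issued twice.** Each number belongs to one labelled vial, and the text describes no copies of the sheet. What is missing is only an account of how the sequence runs across sites.
- **The comparison is biased or the type I error inflated.** Randomisation still protects both; this is chance imbalance and lost precision.

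**Conclusion.** The point holds as a modest weakness in design and analysis. The plan restricts allocation on severity only and names neither severity nor hospital in the model. A noticeable arm imbalance in at least one hospital is likely: about an even chance of a difference of 6 or more patients under the assumed hospital sizes. The precision lost by omitting hospital ranges from about 0 to 9 power points for a six-month level. It is about zero for change from baseline if hospital effects are constant. For the between-group main effect it is 4 to 12 points at between-hospital SDs of 0.4 to 0.7.

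These sizes rest on assumed hospital sizes, between-hospital variances and effect size, none of which the documents give. That the hospitals share the blocks is itself inferred. The change is worth making because it is cheap and has to be settled before the first patient is randomised and before unblinding, not because the trial would be invalid without it.

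**What to change.** **Section 8.2:** pre-specify hospital (three levels) and the severity stratum used in randomisation as fixed effects in every between-arm model, alongside age and sex. Cost: 2 degrees of freedom for hospital and 1 for the stratum, about 1 power point if hospitals do not differ. No extra patients or data are needed.

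**Section 6.3:** state that there is one list per severity stratum, issued centrally, so that each number is used once and in order across the three sites. This leaves hospital unstratified, which is acceptable once hospital is in the model. Small blocks of even size within each hospital and stratum are an optional alternative: they also give balance within hospitals, at the price of six lists and more incomplete blocks. Either route needs a re-cut randomisation list before enrolment starts.

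**Section 6.14:** reconcile Tables 1 and 2 on where faecal calprotectin is measured, since local testing would make the hospital term more important for that endpoint.
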